### 6.2.3 End-of-stimulation

The end-of-stimulation visit will take place when the subject reaches the criterion for triggering of final follicular maturation. Triggering of final follicular maturation will be done either with hCG or GnRH agonist, depending on the extent of ovarian response and whether transfer in the fresh cycle or in a subsequent frozen cycle (including a freeze-all approach) is intended. Administration of REKOVELLE or GONAL-F after reaching the triggering criterion is not allowed.

Criterion for triggering of final follicular maturation with 250 µg hCG:

• ≥3 follicles with a diameter of ≥17 mm and intended transfer in the fresh cycle [*note:* triggering can also be done in case 1 or 2 follicles with a diameter ≥17 mm are observed and the investigator judges that ≥3 follicles with a diameter ≥17 mm cannot be reached, and that triggering is preferred instead of cycle cancellation]

Additional criteria for triggering of final follicular maturation with 0.2 mg GnRH agonist:

- $\geq 25$  follicles with a diameter of  $\geq 12$  mm or
- serum estradiol concentration ≥5,000 pg/mL (18,355 pmol/L) (local laboratory) or
- intended freeze-all approach

Moreover, if these criteria for triggering with GnRH agonist are not met, but the investigator judges that the subject is at risk of developing early OHSS and that triggering with hCG is not advisable, the subject can undergo triggering with GnRH agonist.

In case of poor ovarian response, defined as the investigator judging that the triggering criterion cannot be reached by day 20, the cycle is to be cancelled. In case of excessive ovarian response, defined as the investigator judging that triggering of final follicular maturation is not advisable due to safety concerns, the cycle is to be cancelled.

The investigator also has the option of cancelling the cycle for other relevant medical reasons, including adverse events.

The following must take place at the end-of-stimulation visit:

- Transvaginal ultrasound of ovaries (number and size of follicles)
- Blood collection for central laboratory analysis of endocrine parameters (estradiol, and progesterone)
- Dispensing of hCG or GnRH agonist, as applicable
- Drug accountability of IMP and GnRH antagonist
- Recording of use of any concomitant medication
- Recording of adverse events

For subjects who receive a triggering drug, the next visit is the oocyte retrieval visit which must be scheduled  $36h (\pm 2h)$  after the administration of hCG or GnRH agonist.

Subjects with cycle cancellation will proceed to end-of-trial assessments.

### 6.3 Oocyte Retrieval

Oocyte retrieval must take place 36h ( $\pm$ 2h) after hCG or GnRH agonist administration. All oocytes from follicles with an estimated diameter of  $\geq$ 12 mm must be retrieved. The procedures related to subjects attending the oocyte retrieval visit are listed below, while procedures related to the oocytes are described in section 6.4.

The following must take place at the oocyte retrieval visit:

- Oocyte retrieval
- Drug accountability of hCG or GnRH agonist, as applicable
- Recording of use of any concomitant medication
- Recording of adverse events

For subjects with oocytes retrieved following hCG administration, the next visit is the transfer visit which takes place on day 5 after oocyte retrieval.

For subjects with oocytes retrieved following GnRH agonist no transfer will take place in the fresh cycle. The oocytes will undergo the procedures described in section 6.4 and the blastocysts available on day 5 / day 6 will be cryopreserved in accordance with local guidelines and/or regulations.

Subjects with no oocytes retrieved will proceed to end-of-trial assessments.

#### 6.4 Oocyte / Blastocyst Evaluation

The laboratory procedures regarding handling and evaluation of oocytes and blastocysts are described in a trial-specific manual. This section provides an overview of the oocyte and blastocyst evaluation. The assessment of blastocyst quality is to be performed on the last day of culture. The flow of the trial procedures for oocytes is shown in Table 6-2.

# Table 6-2 Trial Flow Chart – Oocyte / Blastocyst Procedures

	Day 0 (OR)	Day 1 after OR	Day 5 after OR	Day 6 after OR
Oocyte retrieval (OR)	X			
Insemination by IVF and/or ICSI	X			
Assessment of oocyte fertilisation		Х		
Assessment of blastocyst quality a)			Х	Х
Transfer in fresh cycle, if applicable			Х	
Cryopreservation			Х	Х

a) Assessment to be performed on last day of culture only.

ICSI: intracytoplasmic sperm injection, IVF: in vitro fertilisation, OR: oocyte retrieval

#### Assisted hatching is prohibited.

#### Day 0 (Oocyte Retrieval)

- Oocyte retrieval before start of the insemination procedure
- Insemination using IVF or ICSI using ejaculated sperm (fresh or frozen) from partner or donor

#### Day 1 after Oocyte Retrieval

• Assessment of fertilisation

#### Day 5 after Oocyte Retrieval

- Assessment of number and quality of blastocysts based on the Gardner & Schoolcraft blastocyst scoring system^15 [*note:* this assessment is to be performed on last day of culture only]
- Transfer of blastocyst in fresh cycle, if applicable (section 6.6.1)
- Cryopreservation in accordance with local guidelines and/or regulations

# Day 6 after Oocyte Retrieval

- Assessment of number and quality of blastocysts based on the Gardner & Schoolcraft blastocyst scoring system^15 [*note:* this assessment is to be performed on last day of culture only]
- Cryopreservation in accordance with local guidelines and/or regulations

# 6.5 End-of-trial

For subjects who undergo triggering of final follicular maturation, the end-of-trial visit must take place 9-14 days after triggering to cover the assessments of early OHSS (onset  $\leq$ 9 days after triggering).

For subjects who do not undergo triggering of final follicular maturation, the end-of-trial assessments must be performed at the subject's last scheduled trial visit (or alternatively at a separate end-of-trial visit within 7 days of the last scheduled trial visit).

The following end-of-trial procedures / assessments must take place, irrespective of whether the subject discontinues the trial prematurely or completes it:

- Physical examination
- Gynaecological examination
- Recording of use of any concomitant medication
- Recording of adverse events

The assessments serve to document the subject's health at the end of the trial.

# 6.6 Follow-up Assessments

Follow-up assessments are to be performed in the first transfer cycle, irrespective of whether the first transfer takes place in a fresh or frozen cycle. The first transfer cycle covers cycles with transfer occurring within 3 months after start of stimulation. The flow of the follow-up trial procedures is shown in Table 6-3.

-		=	
	Transfer		Clinical pregnancy
	Fresh cycle	Frozen cycle	
	Day 5 after oocyte retrieval	Within 3 months after start of stimulation	5-6 weeks (35-48 days) after transfer
Transfer	Х		
Number and quality of blastocyst(s) transferred	2	K	
Transvaginal ultrasound			Х
Late OHSS a)			Х

#### Table 6-3Follow-up Trial Flow Chart – First Transfer Cycle

a) For subjects who undergo transfer in the fresh cycle, assessment of late OHSS (onset >9 days after triggering) will take place during the follow-up period.

OHSS: ovarian hyperstimulation syndrome

#### 6.6.1 Transfer

The first transfer cycle can take place either in a fresh cycle or in a frozen cycle, as applicable, with the transfer occurring within 3 months after start of stimulation.

#### Blastocyst Transfer in a Fresh Cycle

Transfer is performed on day 5 (blastocyst stage) after oocyte retrieval. Transfer of day 6 (or later) blastocysts is not allowed in the fresh cycle.

The following must take place:

• Transfer of blastocyst(s) [*note:* the number of transferred blastocyst(s) will be based on the subject's wishes and the investigator's recommendation and in accordance with local guidelines and/or regulations]

#### Blastocyst Transfer in a Frozen Cycle

Transfer of cryopreserved blastocyst(s) is performed within 3 months after start of stimulation.

The following must take place:

• Transfer of blastocyst(s) [*note:* the number of transferred blastocyst(s) will be based on the subject's wishes and the investigator's recommendation and in accordance with local guidelines and/or regulations]

#### 6.6.2 Clinical Pregnancy

The subject must attend a visit 5-6 weeks (35-48 days) after the transfer.

The following must take place:

• Transvaginal ultrasound of uterus to assess clinical pregnancy

If at least one gestational sac (either intrauterine or ectopic) is observed, this confirms a clinical pregnancy.

### 6.6.3 Late OHSS

For subjects who undergo transfer in the fresh cycle, the following will take place during the follow-up period:

• Assessment of late OHSS (>9 days after triggering)

# 7 TRIAL ASSESSMENTS

# 7.1 Assessments Related to Primary Endpoint

### 7.1.1 Number of Oocytes Retrieved

The number of oocytes retrieved will be recorded at the oocyte retrieval visit.

#### 7.2 Assessments Related to Secondary Endpoints

### 7.2.1 Number of Follicles (Total and by Size Category) at End-of-stimulation

Transvaginal ultrasound will be performed at the end-of-stimulation visit to count the number of follicles and measure the size of the follicles. Data will be recorded combined for the right and left ovary.

### 7.2.2 Serum Concentrations of Estradiol and Progesterone at End-of-stimulation

Blood samples will be drawn at stimulation day 1 and at end-of-stimulation for measurement of estradiol and progesterone. The sample on stimulation day 1 (baseline) will be collected prior to the first dose of REKOVELLE or GONAL-F.

The samples will be analysed at a central laboratory.

# 7.2.3 Number of Fertilised Oocytes and Fertilisation Rate

The number of pronuclei will be counted after insemination and recorded as 0, 1, 2 or >2. Fertilised oocytes with 2 pronuclei (2PN) will be regarded as correctly fertilised. Fertilisation rate is the number of 2PN oocytes divided by the number of oocytes retrieved.

# 7.2.4 Number of Blastocysts (Total and by Quality)

The number and quality of blastocysts will be assessed on day 5 or day 6 after oocyte retrieval. The quality evaluation of blastocysts on day 5 or day 6 (as applicable) after oocyte retrieval will consist of assessment of three parameters: blastocyst expansion and hatching status, blastocyst inner cell mass grading, and trophectoderm grading. The scoring is based on the classification system by Gardner & Schoolcraft, with the addition of D-categories for inner cell mass and trophectoderm.

Blastocyst expansion and hatching status will be assessed as one of the following:

- 1. An early blastocyst, blastocoel being less than half volume of that of the embryo.
- 2. A blastocyst with a blastocoel whose volume is half of, or greater than half of, that of the embryo.
- 3. A blastocyst with a blastocoel completely filling the embryo.

- 4. An expanded blastocyst with a blastocoel volume larger than that of the early embryo, with a thinning zona.
- 5. A hatching blastocyst with the trophectoderm starting to herniate through the zona.
- 6. A hatched blastocyst, in which the blastocyst has completely escaped from the zona.

For blastocysts with expansion and hatching status 3-6, blastocyst inner cell mass grading and trophectoderm grading will be evaluated.

Blastocyst inner cell mass grading will be assessed as one of the following:

- A. Tightly packed, many cells.
- B. Loosely grouped, several cells.
- C. Very few cells.
- D. Degenerative or no inner cell mass.

Trophectoderm grading will be assessed as one of the following:

- A. Many cells forming a cohesive epithelium.
- B. Few cells forming a loose epithelium.
- C. Very few large cells.
- D. Degenerative or very large cells.

Blastocysts with expansion and hatching status 3-6 will have a score combining the 3 parameters (blastocyst expansion and hatching status, inner cell mass, and trophectoderm); e.g., 4AB for a blastocyst with blastocyst expansion and hatching status 4, inner cell mass grading A, and trophectoderm grading B.

A good-quality blastocyst is defined as a blastocyst of grade 3BB or above.e

# 7.2.5 Total Gonadotropin Dose and Number of Stimulation Days

The administration dates as well as daily dose of IMP will be recorded by the trial medication delegate and used to calculate the total REKOVELLE or GONAL-F dose administered and the number of stimulation days.

<sup>e 3BB and above defined as: 6AA, 6AB, 6AC, 6BA, 6BB, 6BC, 6CA, 6CB, 6CC, 5AA, 5AB, 5AC, 5BA, 5BB, 5BC, 5CA, 5CB, 5CC, 4AA, 4AB, 4AC, 4BA, 4BB, 4BC, 4CA, 4CB, 4CC, 3AA, 3AB, 3AC, 3BA, or 3BB.

# 7.2.6 Early OHSS (Overall and by Grade) and/or Preventive Interventions for Early OHSS

Early OHSS is defined as OHSS with onset  $\leq 9$  days after triggering of final follicular maturation.f Classification of grade is according to Golan's classification system (see section 8.4 for details) and all OHSS cases will be graded as mild, moderate or severe. Preventive interventions for early OHSS cover cycle cancellation due to excessive ovarian response, triggering of final follicular maturation with GnRH agonist (based on the follicular development and/or serum estradiol criteria) and administration of dopamine agonist (the latter is only considered as preventive intervention in subjects with  $\geq 20$  follicles of  $\geq 12$  mm).

### 7.3 Exploratory Assessment

### 7.3.1 Blood Collection for Potential Biomarkers

For subjects who provide additional, optional consent, blood samples will be collected at stimulation day 1 for potential future analysis of possible biomarkers associated with ovarian response.

Results of these potential future exploratory analyses will not be provided to the sites.

# 7.4 Other Assessments

#### 7.4.1 Demographics

Demographic information will be obtained at screening, including the following: date of birthg, ethnicity, race.

# 7.4.2 Medical History

Any relevant medical history will be recorded at screening. This includes diagnoses / symptoms and whether it is a past or ongoing occurrence.

# 7.4.3 Infertility History

Information about the reasons for infertility, duration of infertility, primary infertility and number of previous controlled ovarian stimulation cycles will be obtained at screening.

<sup>f Note this includes OHSS with onset during stimulation or before triggering.

<sup>g Alternatively, age may be recorded in case country-specific restrictions do not permit recording the full date of birth.

# 7.4.4 Body Measurements

Body height and weight will be measured at screening. Body weight will be done without shoes and overcoat and using a calibrated scale.

# 7.4.5 Physical Examination

A complete physical examination will be performed at screening and end-of-trial. Information will be recorded for general appearance, central and peripheral nervous system, head and neck (including ears, eyes, nose, mouth, and throat), respiratory system, cardiovascular system, gastrointestinal system, lymphatic system, urinary system, musculoskeletal system, and skin.

At screening, each category will be evaluated as normal, abnormal not clinically significant or abnormal clinically significant. Abnormal clinically significant findings at screening must be reported in the Medical History Log.

At end-of-trial, potential changes from screening to end-of-trial will be evaluated for each category. In case of changes, these will be evaluated as normal, abnormal not clinically significant or abnormal clinically significant. Abnormal clinically significant changes from screening to end-of-trial must be recorded as adverse events.

# 7.4.6 Gynaecological Examination

A complete gynaecological examination will be performed at screening and end-of-trial. Information will be recorded for breast, external genitalia, vagina, cervix, uterus, ovaries and fallopian tubes.

At screening, each category will be evaluated as normal, abnormal not clinically significant or abnormal clinically significant. Abnormal clinically significant findings at screening must be reported in the Medical History Log.

At end-of-trial, potential changes from screening to end-of-trial will be evaluated for each category. In case of changes, these will be evaluated as normal, abnormal not clinically significant or abnormal clinically significant. Abnormal clinically significant changes from screening to end-of-trial must be recorded as adverse events.

# 7.4.7 Concomitant Medication

The use of any concomitant medication within the last month prior to informed consent for participation in the trial (except medication used in previous infertility treatment cycles) and throughout the trial will be recorded. Recording of concomitant medication will be performed at all visits. Any changes in concomitant medication or treatment must be recorded at each visit.

# 7.4.8 Drug Dispensing and Accountability

The following information will be recorded by the trial medication delegate: 1) dates of administration and daily doses of IMP, 2) time of first IMP administration, 3) dates of administration and daily doses of GnRH antagonist, 4) date and time of administration as well as dose of hCG or GnRH agonist. Details on drug dispensing and accountability are provided in section 5.6.

# 7.5 Assessments Related to Follow-up Information

If a subject achieves a clinical pregnancy after the first transfer cycle, irrespective of whether the first transfer takes place in a fresh or frozen cycle, it will be recorded. Clinical pregnancy will be defined as at least one gestational sac, either intrauterine or ectopic, 5-6 weeks (35-48 days) after transfer. The inclusion of ectopic pregnancies and the lack of specification of heart beat in the definition of clinical pregnancy is in line with the current International Committee Monitoring Assisted Reproductive Technologies (ICMART) and World Health Organization (WHO) glossary on ART terminology.h,16 For intrauterine and ectopic pregnancies, the number of gestational sacs with fetal heart beat as well as without fetal heart beat will be recorded. Vital pregnancy will be defined as at least one intrauterine sac with fetal heart beat 5-6 weeks (35-48 days) after transfer.

The number of blastocysts transferred in the first transfer cycle will also be recorded, allowing for calculation of implantation rate (number of gestational sacs 5-6 weeks (35-48 days) after transfer divided by number of blastocysts transferred).

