### Pregnancy-related Events

The trial includes a follow-up period with collection of data from the subject's first transfer cycle, if the transfer procedure occurs within 3 months after start of stimulation. In this regard, a serious concern associated with ART cycles is the frequency of multiple pregnancies / births and the related neonatal health problems. The number of blastocysts transferred will, for each subject, depend on the local regulations and clinical practice. Participation in this trial does not imply transfer of more blastocysts than what is judged appropriate by the subject, the investigator and local guidelines and/or regulations. The incidence of miscarriage and ectopic pregnancy is higher in women undergoing controlled ovarian stimulation than in women conceiving spontaneously, though the risk of ectopic pregnancy is mainly higher in patients with a history of tubal infertility. Furthermore, the prevalence of congenital malformations after ART may be slightly higher than after spontaneous conceptions; this is thought to be due to differences in parental characteristics (e.g. maternal age and sperm characteristics) and multiple pregnancies.

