#### 8.2 Collection and Recording of Adverse Events

#### 8.2.1 Collection of Adverse Events

The investigator must monitor the condition of the subject throughout the trial from the time of obtaining informed consent until the last visit (end-of-trial visit). In addition, for subjects who undergo transfer in the fresh cycle, assessment of late OHSS (onset >9 days after triggering) will take place during the follow-up period.

The sources of adverse events cover:

- The subject's response to questions about his/her health (a standard non-leading question such as "How have you been feeling since your last visit?" is asked at each visit).
- Symptoms spontaneously reported by the subject.
- Investigations and examinations where the findings are assessed by the investigator to be clinically significant changes or abnormalities.
- Other information relating to the subject's health becoming known to the investigator (e.g. hospitalisation).

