### Trial-specific Source Data Requirements – Ferring

Source documents need to be preserved for the maximum period of time permitted by local requirements. For each subject screened, the investigator will indicate as a minimum in the source documents, that the informed consent is obtained, that the subject participates in this trial, and whether the subject is a screening failure and the reason for screening failure, if applicable. In addition, for each subject randomised the investigator will indicate in the source documents at least the following information, if applicable:

- Existence of subject (initials, date of birth)
- Confirmation of participation in trial (trial ID, subject ID)
- Informed consent (date and time of obtaining written informed consent)
- Eligibility for participation in the trial (documenting all inclusion / exclusion criteria)
- Relevant medical history and infertility history
- Body weight and height
- Visit dates
- Dates and daily doses of IMP
- Dates and daily doses of NIMP
- Dates and dosage regimen of concomitant medication
- Follicular development

- Date of oocyte retrieval and number of oocytes retrieved
- Number and quality of blastocysts
- Adverse events (description as well as start / stop date and time)
- OHSS symptoms, preventive interventions, investigations and treatments
- Reason for discontinuation, if applicable
- Event of unblinding, including the reason for unblinding
- Date of transfer and number of blastocysts transferred (first transfer cycle)
- Ultrasound results at clinical pregnancy visit (first transfer cycle)

No specific protocol data can be recorded directly in the EDC without prior written or electronic record.

If the trial sites use electronic patient record systems, the sponsor will decide if the electronic patient records qualify for the trial and document the decision. If the electronic patient records system does not qualify for the trial, it may be considered to utilise paper data sheets for source data as an exception.

The source data for the endocrine parameters will be available at the central laboratory.

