#### Pregnancy

For subjects with a clinical pregnancy (at least one gestational sac 5-6 weeks after transfer), the type of clinical pregnancy (intrauterine or ectopic) will be described. For subjects with a vital pregnancy (at least one intrauterine gestational sac with fetal heart beat 5-6 weeks after transfer), the number of intrauterine gestational sacs with fetal heart beat will also be described.

Pregnancy rates in the first transfer cycle will be compared between treatments using a logistic regression model with treatment and age group (<35, 35-37, or 38-40 years) as factors. The estimated probabilities, difference in probabilities and 95% CIs for the estimated difference in probabilities will be presented based on the delta method. In these analyses subjects with no transfer or missing data on pregnancy will be regarded as non-pregnant.

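### An ectopic pregnancy diagnosed and treated before the day 35-48 visit enters neither the pregnancy-type table nor the adverse-event tables, so the by-arm ectopic count is biased low.

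*Combined protocol and SAP*

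**What the plan says.** **Intention.** Section 1.3 of the protocol names the risk: "The incidence of miscarriage and ectopic pregnancy is higher in women undergoing controlled ovarian stimulation than in women conceiving spontaneously". Section 7.5 includes ectopics in clinical pregnancy, "Clinical pregnancy will be defined as at least one gestational sac, either intrauterine or ectopic, 5-6 weeks (35-48 days) after transfer", and says their inclusion agrees with an international glossary. The glossary text, given in a footnote, has no day window and also accepts definite clinical signs. SAP section 10.4 states that for subjects with a clinical pregnancy "the type of clinical pregnancy (intrauterine or ectopic) will be described".

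**Ascertainment.** Section 6.6.2 prescribes one visit 35-48 days after transfer and one procedure, "Transvaginal ultrasound of uterus to assess clinical pregnancy". It continues: "If at least one gestational sac (either intrauterine or ectopic) is observed, this confirms a clinical pregnancy". In the source-data list of section 10.1, the only entry on pregnancy outcome is "Ultrasound results at clinical pregnancy visit (first transfer cycle").

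**Adverse events.** Under section 8.2.1 the investigator monitors the subject "throughout the trial from the time of obtaining informed consent until the last visit (end-of-trial visit"). Section 6.5 sets that visit at 9-14 days after triggering. During follow-up the only event actively assessed is late OHSS, and only after a fresh transfer. Section 8.6.2 keeps reporting open for later serious events, but only those judged to have a reasonable possible causal link to the IMP or to an NIMP for which the sponsor holds the marketing authorisation. Treatment-emergent events are bounded by the end-of-trial visit (protocol 9.9, SAP 11.2).

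**Analysis.** SAP sections 10 and 10.4 treat absent pregnancy data as not pregnant.

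**The concern.** The plan sets out to describe ectopic pregnancies by treatment arm, yet its only means of finding one is a scan five to seven weeks after transfer. If an ectopic has been diagnosed and treated by then, no sac remains to be seen, and no other planned route leads to a table. Nothing in either document tells sites to record an ectopic diagnosed earlier.

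The stake is safety and outcome reporting. Few ectopics are expected, so missing even one or two changes the count materially. A low or zero count could be read as reassurance when it partly reflects when subjects were asked.

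**Working it through.** **Figures in the plan.** The documents state no pregnancy or ectopic rate, so there is no figure on this point to reproduce. The one design figure, the half-width for the oocyte difference, reproduces: 1.96 × 6.0 × √(1/200 + 1/100) = 1.44. Nothing below depends on it.

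**Timeline, fresh transfer.** Inputs: retrieval 36 h (±2 h) after triggering (6.3); transfer on day 5 after retrieval (6.6.1); end-of-trial visit 9-14 days after triggering (6.5); pregnancy visit 35-48 days after transfer (6.6.2).

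- Trigger to transfer: 1.5 + 5 = 6.5 days.
- End-of-trial visit, counted from transfer: 9 − 6.5 = 2.5 days to 14 − 6.5 = 7.5 days.
- Interval without general event collection: shortest 35 − 7.5 = 27.5 days; longest 48 − 2.5 = 45.5 days.
- If the end-of-trial visit is postponed by the permitted one day: 15 − 6.5 = 8.5 days after transfer, and a shortest interval of 35 − 8.5 = 26.5 days.
- The ±2 h tolerance on retrieval moves these figures by less than 0.1 day.

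**Timeline, frozen transfer.** Transfer may occur up to 3 months after the start of stimulation. If it follows the end-of-trial visit, no general event collection takes place after transfer at all.

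**Tracing one case.** Take an ectopic diagnosed and treated after the end-of-trial visit and before the pregnancy visit.

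| Planned output | What happens | Source |
|---|---|---|
| Pregnancy rate | Counted as not pregnant: no sac at the visit, or visit missed and set to negative | Protocol 7.5, 9.11; SAP 10, 10.4 |
| Pregnancy by type | Absent: table limited to subjects meeting the 5-6 week definition | SAP 10.4 |
| Treatment-emergent events | Absent if onset is after the end-of-trial visit | Protocol 9.9; SAP 11.2 |
| Late serious events | Reported to the sponsor only if serious and judged related; no planned table | Protocol 8.6.2; SAP 11.2 |

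**Expected number of ectopics (assumed rates).** Expected cases = 300 × clinical pregnancy rate × ectopic share.

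- 30% and 1%: 300 × 0.30 × 0.01 = 0.9.
- 40% and 3%: 300 × 0.40 × 0.03 = 3.6.
- Wider range, 25% and 1% to 45% and 4%: 300 × 0.25 × 0.01 = 0.75 to 300 × 0.45 × 0.04 = 5.4.
- Chance of at least one ectopic over the wider range: 1 − (1 − 0.0025)^300 = 0.53 to 1 − (1 − 0.018)^300 = 0.996.

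These are all ectopics in both arms together. They cap the number lost, because an ectopic whose sac is still seen at days 35-48 is counted.

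**Weight of one case in the pregnancy rate.** 1/200 = 0.5 percentage points with REKOVELLE; 1/100 = 1.0 with GONAL-F. The 95% half-width for the difference, 1.96 × √[p(1 − p)(1/200 + 1/100)], is 10.4 points at p = 0.25, 11.4 at 0.35 and 11.9 at 0.45.

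**The case against.** The strongest reply is that clinical pregnancy here is a time-point measure, stated consistently in both documents as a sac at 5-6 weeks. A subject without one is scored exactly as defined, an intrauterine pregnancy lost before day 35 is treated the same way, and the rule is identical in both arms. That stands. A reader might infer that these subjects are misclassified in the pregnancy comparison, but the definition does not support that. The fair remark is that the definition is narrower than the glossary the protocol says it follows.

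Three other inferences go too far:

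- **That ectopics are not looked for, because section 6.6.2 specifies a scan of the uterus.** The next sentence of that section accepts an ectopic sac, section 7.5 requires sacs to be recorded for ectopic pregnancies, and section 3.1.2 speaks of transvaginal ultrasound without that restriction.
- **That an ectopic persisting to the visit is wrongly scored as a success.** Section 7.5 discloses and explains this choice, and vital pregnancy, which requires an intrauterine sac with heart beat, is described separately.
- **That all adverse-event reporting stops.** Section 8.6.2 has no time limit for related serious events, so a treated ectopic could reach the sponsor's pharmacovigilance function. It still would not reach a planned table.

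It is also fair to say that the eCRF is not among the documents, so the pregnancy form may ask more than the protocol requires. Pregnancy is a follow-up assessment, all analyses are descriptive, and counts this small support no inference between arms. These points limit the weight of the concern. None of them supplies a written route for recording and tabulating an ectopic treated earlier.

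**Conclusion.** The gap is real and narrow. Followed exactly, the plan undercounts ectopic pregnancies in both arms, because cases diagnosed and treated between the end-of-trial visit and the pregnancy visit have no planned place in the tables. The documents give no reason to expect the loss to differ between arms.

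The timeline rests on the protocol's own visit windows. The 1-4 expected ectopics (0.75-5.4 over the wider range) rest on assumed rates. How many would be lost depends on the share treated before the visit. The documents do not give that share, so they do not support a claim that the count would be lost entirely. The pregnancy comparison would barely move, and the primary endpoint, secondary endpoints and sample size are unaffected. This is a completeness improvement to safety and outcome reporting.

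**What to change.** 1. **Protocol 6.6.2 and 7.5:** at the existing pregnancy visit, record whether an ectopic pregnancy was diagnosed or treated at any time since transfer, with the date. Add the item to the source-data list in section 10.1.
2. **SAP 10.4:** tabulate or list all ectopics by arm whatever the date of diagnosis, separating those seen at the visit from those diagnosed earlier.
3. **Both documents:** leave the 5-6 week definitions of clinical pregnancy and implantation unchanged, and state that they are narrower than the quoted glossary definition, which has no day window.

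Earlier ectopics should not be added to the clinical pregnancy rate. Intrauterine losses before day 35 would stay negative, so one endpoint would have two time rules. The implantation analysis would also contain clinical pregnancies with zero sacs.

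The cost is one eCRF question, one descriptive table or listing, and short wording changes in the protocol and SAP. No visit or procedure is added. The question will still miss subjects who do not attend the visit, and the table should carry that note.
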